 28. Female subjects who are breastfeeding or pregnant at Screening or Baseline (as documented by a positive β -human chorionic gonadotropin test). A separate Baseline assessment is required if a negative screening pregnancy test was obtained more than 72 hours before the first dose of study drug.
 29. Female subjects of childbearing potential who:
 - a. Had unprotected sexual intercourse within 30 days before study entry and who do not agree to use a highly effective method of contraception (eg, total abstinence, an intrauterine device, a double-barrier method [such as condom plus diaphragm with spermicide], a contraceptive implant, an oral contraceptive, or have a vasectomized partner with confirmed azoospermia) throughout the entire study period and for 28 days after study drug discontinuation
 - b. Are currently abstinent and do not agree to use a double-barrier method (as described above) or refrain from sexual activity during the study period and for 28 days after study drug discontinuation
 - c. Are using hormonal contraceptives, but are not on a stable dose of the same hormonal contraceptive product for at least 4 weeks before dosing and who do not agree to use the same contraceptive during the study and for 28 days after study drug discontinuation
- (NOTE: All female subjects will be considered to be of childbearing potential unless they have been sterilized surgically [ie, bilateral tubal ligation, total hysterectomy, or bilateral oophorectomy, all with surgery at least 1 month before dosing]).

Study Treatment(s)**Test drug**

Belviq XR (lorcaserin hydrochloride) will be provided as orange-colored, round, film-coated, biconvex tablets with one 20-mg tablet administered orally QD.

Comparator Drug

Matching placebo, 1 tablet administered orally QD

Duration of Treatment

Prerandomization Phase: up to 30 days

Randomization Phase: approximately 56 weeks

Concomitant Drug/Therapy

Other products intended for weight loss, including prescription drugs, OTC drugs, and herbal preparations, are prohibited as concomitant medications. OTC cold medicines containing dextromethorphan can be used for up to 7 days with study medication temporarily stopped for that time period and resumed the next day after the OTC cold medicine is stopped. Any of the following serotonergic agents or other agents in combination with Belviq XR are prohibited:

Serotonergic drugs

- SSRIs
- SNRIs
- TCAs
- bupropion
- triptans
- St. John's Wort
- tryptophan
- MAOIs
- linezolid

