9 INVESTIGATIONAL PLAN

9.1 Overall Study Design and Plan

This is a multicenter, randomized, double-blind, placebo-controlled, parallel-group study in obese adolescents ages 12 to 17 years. Approximately 260 subjects will be randomized in a 1:1 ratio to Belviq XR 20 mg QD (130 subjects) and placebo (130 subjects). Subjects will be stratified by sex. Subjects will receive Belviq XR 20 mg or placebo QD in a 1:1 ratio for up to 52 weeks. Throughout the duration of the study, subjects will be encouraged to adhere to a lifestyle modification program that includes a standardized, age-appropriate diet and exercise counseling (see [Appendix 2](#)). (revised per Amendment 02)

The study will consist of 2 phases: Prerandomization and Randomization. The Prerandomization Phase will last up to 30 days and consists of 1 visit during which subjects will be screened for eligibility. The Randomization Phase consists of a Treatment Period and a Follow-Up Period. The Treatment Period will last for a maximum of 52 weeks, with visits at Weeks 1, 5, 8, 12, 20, 28, 36, 44, and 52; the Follow-Up Period will extend from the End of Treatment (EOT) visit to the End of Study (EOS) visit.

Subjects who screen fail can be rescreened only once after 60 days. All subjects will continue in the study until the 52-week evaluation is completed. Subjects who discontinue treatment prematurely will be followed up until study completion.

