Table 2 Schedule of Procedures/Assessments in Study APD356-A001-403 (revised per Amendments 01 and 02)															
Phase:	Prerandomization^a	Randomization													
Period:	Screening	Treatment											Follow-Up		
Visit Number:	1	2 ^a	3	4	5	6	7	8	9	10	11 (EOT)	EOS	US ^b	ED	
Day:	-30 to -1	1													
Weeks^{c,d}:		0	1	5	8	12	20	28	36	44	52	56			
Procedure															

AE = adverse event, AM = morning; CDC = Centers for Disease Control and Prevention, C-SSRS = Columbia-Suicide Severity Rating Scale, ECG = electrocardiogram, ED = early discontinuation, EOS = End of Study, EOT = End of Treatment, HbA_{1c} = hemoglobin A1c, IxRS = interactive voice or web response system, NTX = N-telopeptide, OC = osteocalcin; PHQ-9 = The Patient Health Questionnaire, PICP = carboxyterminal propeptide of type I procollagen, PD = pharmacodynamic, PK = pharmacokinetics, SAE = serious adverse event; T4 = thyroxine, TSH = thyroid stimulating hormone, US = unscheduled.

- ^a: Baseline measurements will be collected on Day 1, before drug administration unless specified otherwise.
- ^b: Unscheduled visits may be conducted at any time that additional assessments are indicated in the clinical judgment of the investigator. Note that not all assessments listed under Unscheduled Visit need to be conducted – actual assessments needed will be determined by the investigator and will be based on the specific visit needs. At Unscheduled Visits, PK samples should only be collected if subject has experienced a serious adverse event (SAE) while on study drug and the sample can be drawn within 60 hours of the initiation of the SAE. (revised per Amendment 01)
- ^c: Window ±7 days for all visits. (revised per Amendment 01)

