- ^d: On the day of the Week 12, 28, and 52 clinic visits, subjects will be instructed not to take their study drug at home before the visit, but to bring their study drug to the clinic visit and take their daily dose at the clinic. Two blood samples for determination of plasma concentrations of lorcaserin will be taken: 1 predose (within 30 minutes before dosing) and 1 within 1 to 3 hours after dosing. Dose times must be recorded for the last 2 dosing times before the day of clinic visit. Week 52 PK samples should only be collected if the sample can be drawn within 60 hours of the last dose of study drug. On the day of the Week 36 clinic visit, subjects will take the morning dose at home, and will be asked to visit the clinic within 4 to 6 hours of dosing that day, during which 1 blood sample for PK assessments will be collected. Dose times must be recorded for the last 2 dosing times prior to the clinic visit. (revised per Amendment 01)
- ^e: Includes a neuromuscular assessment and signs and symptoms of priapism (painful erection) and hyperprolactinemia (menstrual cycle abnormalities or galactorrhea) (revised per Amendment 01)
- ^f: PK samples should only be collected if the sample can be drawn within 60 hours of the last dose of study drug.
- ^g: PK samples should only be collected if subject has experienced an SAE while on study drug and the sample can be drawn within 60 hours of the initiation of the SAE.
- ^h: Echocardiographic assessments will be performed during screening period after subjects have met all other inclusion and exclusion criteria.
- ⁱ: Lifestyle modification counseling will also be performed at Weeks 3, 16, 24, 32, 40, and 48 in addition to counseling at the scheduled visits in [Appendix 2](#).

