9.5.4.2 Reporting of Pregnancy and Exposure to Study Drug through Breastfeeding

Any pregnancy in which the estimated date of conception is either before the last visit or within 28 days of last study treatment or any exposure to study drug through breastfeeding during study treatment or within 28 days of last study treatment must be reported.

If an adverse outcome of a pregnancy is suspected to be related to study drug exposure, this should be reported regardless of the length of time that has passed since the exposure to study treatment.

A congenital anomaly, death during perinatal period, an induced abortion, or a spontaneous abortion are considered to be an SAE and should be reported in the same time frame and in the same format as all other SAEs (see [Section 9.5.4.1](#)).

Pregnancies or exposure to study drug through breastfeeding must be reported by fax or email as soon as possible but no later than 1 business day from the date the investigator becomes aware of the pregnancy. The contact information for the reporting of pregnancies and exposure to study drug through breastfeeding is provided in the Investigator Study File. The Pregnancy Report Form must be used for reporting. All pregnancies must be followed to outcome. The outcome of the pregnancy must be reported as soon as possible but no later than 1 business day from the date the investigator becomes aware of the outcome.

A subject who becomes pregnant must be withdrawn from the study.

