9.7.1.8 Safety Analyses

Evaluations of safety will be performed on the Safety Analysis Set. Safety assessments including the incidence of AEs (including changes from baseline in physical examination, neuromuscular sign assessment, and signs and symptoms of priapism and hyperprolactinemia), out-of-normal-range laboratory safety test values, change from baseline in laboratory safety test values, ECGs, and vital sign measurements will be summarized by treatment group using descriptive statistics or frequency count as appropriate. (revised per Amendment 01)

No hypothesis testing will be performed for the safety assessment.

Study Day 1 for all safety analyses will be defined as the date of the 1st dose of study drug.

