9.7.1.8.2 ADVERSE EVENTS

The AE verbatim descriptions (investigator terms from the CRF) will be classified into standardized medical terminology using the Medical Dictionary for Regulatory Activities (MedDRA). Adverse events will be coded to the MedDRA (Version 18.0 or higher) lower level term closest to the verbatim term. The linked MedDRA PT and primary system organ class (SOC) are also captured in the database.

A treatment-emergent AE (TEAE) is defined as an AE that emerges during treatment (up to 28 days after the last dose of study drug), having been absent at pretreatment (Baseline) or

- Reemerges during treatment (up to 28 days after the last dose of study drug), having been present at pretreatment (Baseline) but stopped before treatment, or
- Worsens in severity during treatment relative to the pretreatment state, when the AE is continuous.

Only those AEs that were treatment emergent will be included in summary tables. All AEs, treatment emergent or otherwise, will be presented in subject data listings.

The TEAEs will be summarized by treatment group. The following summaries will be reported for TEAEs:

- Incidence of TEAEs in descending order of frequency
- Incidence of TEAEs by SOC and PT
- Incidence of treatment-related TEAEs by SOC and PT
- Incidence of TEAEs by SOC, PT and maximum severity (mild, moderate, or severe)
- Incidence of treatment-related TEAEs by SOC, PT, and maximum severity (mild, moderate, or severe)
- Incidence of TEAEs by SOC, PT, and relationship to study drug (Yes [related] or No [not related])

A subject will be counted only once within a SOC or PT, if the subject experienced more than 1 TEAE within a specified SOC and PT.

The following summaries will also be presented for the treatment-emergent SAEs.

- Incidence of TEAEs leading to death
- Incidence of treatment-emergent SAE by SOC and PT
- Incidence of treatment-related treatment-emergent SAE by SOC and PT

In addition, subjects with TEAEs leading to discontinuation from study drug and AEs of special interest as described in [Section 9.5.4.3.2](#) will be summarized by MedDRA SOC and PT for each treatment group.

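### The ±7-day window on every visit lets the Week 56 End of Study visit fall before the protocol's own 28-day post-dose period has ended

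*Protocol*

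**What the plan says.** All references are to the current protocol (v7.0).

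- **Window.** Section 9.5.2.1, Table 2, footnote c: "Window ±7 days for all visits". No visit is excepted, and the footnote does not say what the EOS window is counted from.
- **Calendar.** Section 9.7.1.8: "Study Day 1 for all safety analyses will be defined as the date of the 1st dose of study drug". Table 2, footnote a: "Baseline measurements will be collected on Day 1, before drug administration unless specified otherwise". Section 9.1 lists the treatment period "with visits at Weeks 1, 5, 8, 12, 20, 28, 36, 44, and 52" and caps it at 52 weeks. The Synopsis gives "Randomization Phase: approximately 56 weeks", and Table 2 places EOS at Week 56. Section 9.1 runs the Follow-Up Period from the EOT visit to the EOS visit but gives no interval in days.
- **Last dose.** Table 2, footnote d has the Week 52 dose taken at the clinic visit.
- **28-day post-dose period.** Section 9.7.1.8.2: "A treatment-emergent AE (TEAE) is defined as an AE that emerges during treatment (up to 28 days after the last dose of study drug". Section 9.5.4.2 requires reporting of "Any pregnancy in which the estimated date of conception is either before the last visit or within 28 days of last study treatment". Section 9.5.1.5.1 follows AEs for 28 days after the last dose or until resolution, and collects SAEs for 28 days. Section 9.5.4.1 collects SAEs through the last visit and for 28 days after the last dose.
- **EOS content.** Table 2 schedules AE monitoring, physical examination, laboratory tests, urine pregnancy test, ECG, C-SSRS and PHQ-9 at EOS. No later visit is scheduled.
- **Week 1.** Visit 3 includes the physical examination. Footnote e describes it: "Includes a neuromuscular assessment and signs and symptoms of priapism (painful erection) and hyperprolactinemia". The next scheduled examination is at Week 12.

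**The concern.** The follow-up visit appears to have been placed at Week 56 so that it closes the 28-day period after treatment. A symmetric window around a visit that sits exactly on that boundary works against this: about half of the permitted days lie before the period is over.

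What is at stake is scheduled safety coverage in adolescents. If EOS comes early, the last planned AE review, pregnancy test, laboratory tests, ECG, C-SSRS and PHQ-9 are done while the period for counting treatment-emergent events and reporting pregnancies is still open. Anything that happens in the remaining days reaches the database only if the site or family initiates contact.

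**Working it through.** **Step 1. Nominal days.** Day = 1 + 7 × week, with Day 1 the date of first dose.

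- Week 1: 1 + 7 = Day 8
- Week 12: 1 + 84 = Day 85
- Week 52 (EOT): 1 + 364 = Day 365
- Week 56 (EOS): 1 + 392 = Day 393

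The nominal EOT-to-EOS gap is 393 − 365 = 28 days. This reproduces the protocol's 28-day period exactly, so there is no slack.

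**Step 2. Apply ±7 days.** Footnote c gives no anchor for EOS, so three readings have to be checked.

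| Reading | Shortest gap | Permitted days short of 28 |
|---|---|---|
| A. EOS timed from the actual EOT visit | 28 − 7 = 21 days after EOT | 7 of 15 (−7 to −1) |
| B. EOS on the Day 1 calendar, dosing stops at 52 × 7 = Day 364 | 386 − 364 = 22 days after last dose | 6 of 15 (−7 to −2) |
| C. EOT and EOS both on the Day 1 calendar, last dose at the EOT visit | 386 − 372 = 14 days after last dose | 105 of 225 pairs |

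In reading C, EOT may fall on Days 358 to 372 and EOS on Days 386 to 400, so the gap runs from 14 to 400 − 358 = 42 days. There are 15 × 15 = 225 pairs of permitted days. The gap is below 28 whenever the EOS deviation is smaller than the EOT deviation: (225 − 15)/2 = 105 pairs. Of these, 14 + 13 + 12 + 11 + 10 + 9 = 69 are short by only 1 to 6 days. Only one pair in 225 gives 14 days.

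That pair needs a dose on Day 372, which is beyond the 52-week maximum treatment period in Section 9.1. The window, the clinic dose at Week 52 and the 52-week maximum have to be reconciled with one another.

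**Step 3. Which duties depend on the visit.** SAE collection and pregnancy reporting are defined by days since the last dose, and AE follow-up by days since the last dose or resolution. None of them ends because EOS has taken place. What an early EOS removes is the scheduled contact and tests for the remaining days: up to 28 − 21 = 7 days in reading A, 28 − 22 = 6 in reading B, and 28 − 14 = 14 in the extreme of reading C.

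**Step 4. Week 1 (secondary).** Day 8 ± 7 is Day 1 to Day 15, so the window formally touches Visit 2 on Day 1. The scheduled gap from the Week 1 examination to Week 12 is nominally 85 − 8 = 77 days. With Week 1 at −7 and Week 12 at +7 (Day 92) it becomes 92 − 1 = 91 days, 14 days longer.

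**The case against.** The strongest reply is that the follow-up itself is not lost. SAEs are collected for 28 days after the last dose whatever the date of EOS, AEs already open are followed for 28 days or until resolution, pregnancy reporting depends on the conception date, contraception is required for 28 days after discontinuation, and unscheduled visits may be made at any time. This stands, and it limits the point to scheduled coverage. One qualification: Section 9.5.1.5.1 collects new non-serious AEs only through the last visit of the Treatment Phase, so for those the EOS contact matters more than the reply allows.

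Four stronger readings are tempting and are not supported:

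- **That EOS will typically be 14 days after the last dose.** This is one permitted pair in 225. It also requires both windows to run from Day 1, which footnote c does not state, and dosing past the 52-week maximum.
- **That 47% of completers would have a short follow-up.** 105/225 = 47% counts permitted pairs of days. It becomes a forecast only if visit deviations are independent and uniform, and nothing in the protocol supports that.
- **That an early Week 1 visit leaves neuropsychiatric effects unassessed until Week 12.** AE monitoring, C-SSRS and PHQ-9 recur at Weeks 5 and 8. Only the structured neuromuscular examination waits, and it already waits 77 days in the nominal schedule. Serotonin syndrome is in any case always reportable as serious.
- **That EOS data are spoiled by mixing different times off drug.** Analysis visit windows are commonly left to the SAP, no efficacy endpoint uses Week 56, and safety is summarized without hypothesis tests.

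**Conclusion.** The point holds as a minor inconsistency between the visit schedule and the protocol's own 28-day period. On each of the three readings of the window, a fully compliant EOS visit can come before Day 28. The minimum is 21 days after EOT if timed from EOT, 22 days after the last dose under the 52-week cap, and 14 days only in the extreme case that conflicts with that cap. Reading A equals time since last dose only if the Week 52 dose is taken at the EOT visit, as footnote d provides. How often EOS would actually be early cannot be stated from the document.

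The consequence is a few days without scheduled contact or tests, not the end of any reporting duty. The primary endpoint and the stated power are unaffected. The Week 1 window is a remark only: its lower end should not coincide with first dose, but the protocol offers no basis for a particular width.

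**What to change.** Amend Table 2, footnote c for EOS and leave the other visits as they are, apart from Week 1:

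- **Subjects who complete treatment:** EOS is timed from the actual EOT visit or last dose, whichever is later, and takes place no earlier than 28 days after it, with a plus-side window only (for example 0 to +7 days).
- **Subjects who stop study drug early:** the Week 52 evaluation and the Week 56 EOS stay on the randomization calendar. Timing their EOS from the last dose would be wrong. For a subject stopping at Week 12 it would fall at Week 16, before the primary endpoint visit that Sections 9.1 and 9.5.5 require.
- **Reconcile** the Week 52 window and clinic dose with the 52-week maximum treatment period.
- **Week 1:** the sponsor should set a narrower window that cannot coincide with first dose and give its reason for the width chosen.

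The cost is one footnote, an EOS visit a few days later for some subjects, and slightly less booking flexibility.

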9.5.2.2 Description of Procedures/Assessments Schedule

Please refer to the Schedule of Assessments ([Table 2](#)) for details, giving particular attention to all footnotes.

9.5.2.3 Total Volume of Blood Sampling

Table 3 presents the number of blood samples and the total volume of blood that will be collected throughout the study. Additional samples may be taken at the discretion of the investigator if the results of any tests fall outside reference ranges or clinical symptoms necessitate testing to ensure subject safety.

Table 3 Summary of Blood Sample Volumes (revised per Amendment 01)

	Sample Volume per Collection (mL)	Number of Collection Time Points	Total Volume Collected (mL)
Clinical laboratory tests (Chemistry and Hematology)	5	Screening: 1 Visits 2, 3, 4, 6, 8, 11 (EOT), EOS or ED	5×8=40
T4, TSH, AM Serum Cortisol, Testosterone, estradiol	6	Screening: 1 Visits 8, 11 (EOT), or ED	6×3=18
Serum OC and PICP, Hydroxy-proline; Fasting lipid panel (HDL cholesterol, LDL cholesterol, total cholesterol, triglycerides)	8	Visits 2, 8, 11 (EOT), or ED	8×3=24
Fasting Prolactin, FPG, fasting insulin, and HbA _{1c} sampling	5	Screening: 1 Visits 2, 6, 8, 11 (EOT) or ED	5×5=25
PK/PD blood sampling	4	Visits 6, 8, and 11 (EOT) or ED (2 samples each); Visit 9 (1 sample only)	7×4=28
Total			135

ED= early discontinuation from study, EOS = End of Study, EOT = End of Treatment, FPG = fasting plasma glucose, HbA_{1c} = hemoglobin A_{1c}, OC = osteocalcin, PD = pharmacodynamic, PICP = carboxyterminal propeptide of type I procollagen, PK = pharmacokinetics, T4 = thyroxine, TSH = thyroid stimulating hormone.

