9.5.1.5.3 LABORATORY MEASUREMENTS

Clinical laboratory tests to be performed, including hematology, chemistry, and urinalysis, are summarized in [Table 1](#). Subjects should be in a seated or supine position during blood collection. The Schedule of Procedures/Assessments ([Table 2](#)) shows the visits and time points at which blood for clinical laboratory tests and urine for urinalysis will be collected in the study.

Table 1 Clinical Laboratory Tests (revised per Amendment 01)

Category	Parameters
Hematology	Hematocrit, hemoglobin, platelets, RBC count, and WBC count with differential (bands, basophils, eosinophils, lymphocytes, monocytes, neutrophils)
Chemistry	
Electrolytes	Chloride, potassium, sodium
Liver function tests	Alanine aminotransferase, alkaline phosphatase, aspartate aminotransferase, gamma glutamyl transpeptidase, direct bilirubin, total bilirubin
Renal function tests	Blood urea/blood urea nitrogen, creatinine
Thyroid function	T4, TSH
Adrenal function	AM serum Cortisol
Sex hormones	Testosterone (male subjects), estradiol (female subjects)
Bone health assessments	Serum OC and PICP, Hydroxy-proline; Urine NTX
Prolactin	Fasting prolactin levels
Other (revised per Amendment 01)	Albumin, calcium, globulin, fasting glucose, HbA _{1c} , HDL cholesterol, fasting insulin, lactate dehydrogenase, LDL cholesterol, fasting lipid panel, phosphorus, total protein, total cholesterol, triglycerides, uric acid, urine β -hCG
Urinalysis	Bacteria, casts, crystals, epithelial cells, glucose, ketones, occult blood, pH, protein, RBCs, specific gravity, WBCs

β -hCG = beta-human chorionic gonadotropin, HbA_{1c} = hemoglobin A_{1c}, HDL = high density lipoprotein, LDL = low density lipoprotein, OC = osteocalcin; NTX = N-telopeptide, PICP = carboxyterminal propeptide of type I procollagen; RBC = red blood cell, T4 = thyroxine, TSH = thyroid stimulating hormone, WBC = white blood cell.

Clinical laboratory tests during the study will be performed by a central laboratory. All blood and urine samples will be collected and sent to the central laboratory on the day of collection unless otherwise instructed. In cases of a safety concern, blood samples will be split (or 2 samples drawn) to allow a local laboratory analysis in addition to the central laboratory.

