9.5.2 Schedule of Procedures/Assessments**9.5.2.1 Schedule of Procedures/Assessments**

[Table 2](#) presents the Schedule of Procedures/Assessments for the study.

Table 2 Schedule of Procedures/Assessments in Study APD356-A001-403 (revised per Amendments 01 and 02)															
Phase:	Prerandomization^a	Randomization													
Period:	Screening	Treatment											Follow-Up		
Visit Number:	1	2 ^a	3	4	5	6	7	8	9	10	11 (EOT)	EOS	US ^b	ED	
Day:	-30 to -1	1													
Weeks^{c,d}:		0	1	5	8	12	20	28	36	44	52	56			
Procedure															
Informed Consent	X														
Demography	X														
Medical History	X														
Prior/concomitant medication assessments	X	X	X	X	X	X	X	X	X	X	X	X	X	X	
AE monitoring	X	X	X	X	X	X	X	X	X	X	X	X	X	X	
Inclusion/exclusion criteria	X	X													
Physical Examination ^e	X	X	X			X		X			X	X	X	X	
Vital signs	X	X	X	X	X	X	X	X	X	X	X	X	X	X	
Height	X	X	X	X	X	X	X	X	X	X	X	X	X	X	
Weight	X	X	X	X	X	X	X	X	X	X	X	X	X	X	
Waist circumference	X	X		X		X		X	X		X	X	X	X	
CDC growth chart	X	X		X		X		X	X		X	X	X	X	
Tanner Staging	X	X						X			X	X	X	X	
Routine clinical laboratory tests	X	X	X	X		X		X			X	X	X	X	
Urinalysis	X	X	X	X		X		X			X	X	X	X	
Urine drug and cotinine test	X														
Fasting plasma glucose, insulin, and HbA1c sampling	X	X				X		X			X			X	
T4 and TSH	X							X			X			X	
Testosterone, Estradiol	X							X			X				

Phase:	Prerandomization ^a	Randomization													
Period:	Screening	Treatment											Follow-Up		
Visit Number:	1	2 ^a	3	4	5	6	7	8	9	10	11 (EOT)	EOS	US ^b	ED	
Day:	-30 to -1	1													
Weeks ^{c,d} :		0	1	5	8	12	20	28	36	44	52	56			
Procedure															
Pregnancy test (urine)	X	X	X	X	X	X	X	X	X	X	X	X		X	
Fasting prolactin	X	X				X		X			X			X	
OC, PICP, and Hydroxy-proline		X						X			X			X	
Fasting lipid panel		X						X			X			X	
Urine NTX		X						X			X			X	
PK/PD blood sampling						X		X	X		X ^f		X ^g	X ^f	
AM serum cortisol		X									X			X	
ECG		X						X			X	X		X	
Echocardiograph	X ^h							X			X			X	
Randomization		X													
IxRS	X	X		X	X	X	X	X	X	X	X				
Study drug dispensing		X		X	X	X	X	X	X	X			X		
Collect study medication				X	X	X	X	X	X	X	X	X	X	X	
Drug accounting and compliance			X	X	X	X	X	X	X	X	X		X	X	
Hand x-ray for bone age		X				X		X			X			X	
C-SSRS	X		X	X	X	X	X	X	X	X	X	X	X	X	
Leiter-3		X		X				X			X	X		X	
PHQ-9		X	X	X	X	X	X	X	X	X	X	X	X	X	
Standardized age-appropriate lifestyle modification counseling ⁱ		X	X	X	X	X	X	X	X	X			X		

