9.5.5 Completion/Discontinuation of Subjects

The investigator may withdraw the subject from the study at any time for safety or administrative reasons. A subject may elect to discontinue the study at any time for any reason. All subjects will continue in the study until the 52-week evaluation is completed. Subjects who discontinue treatment prematurely will be followed up until study completion. All subjects who discontinue the study are to complete the study's early discontinuation procedures indicated in the Schedule of Procedures/Assessments [Table 2](#)).

The investigator will promptly explain to the subject involved that the study will be discontinued for that subject and provide appropriate medical treatment and other necessary measures for the subject. A subject who has ceased to return for visits will be followed up by mail, phone, or other means to gather information such as the reason for failure to return, the status of treatment compliance, the presence or absence of AEs, and clinical courses of signs and symptoms.

Subjects who discontinue early from the study will be discontinued for 1 of these primary reasons: AE(s), lost to follow-up, subject choice, withdrawal of consent, pregnancy, study terminated by sponsor, or other. In addition to the primary reason, the subject may indicate 1 or more of secondary reasons for discontinuation. Study disposition information will be collected on the Subject Disposition CRF.

Detailed retention strategies will be developed and included in study manual. These include a highly trained and competent staff, easy access to the clinic, reminder and follow-up calls, interactive group sessions with games and hands-on nutrition and physical activity demonstrations, random raffle drawings, social events, birthday and holiday cards, and newsletters. In addition, home visits for assessments of families will be an option, as needed, to maximize data collection. This detailed retention plan will help prevent missing data.

A subject removed from the study for any reason may not be replaced.

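### Tables 2 and 3 disagree on when sex hormones and morning cortisol are drawn, and the controlling Table 2 takes no sex-hormone sample at early discontinuation

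*Protocol*

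**What the plan says.** Table 3 (Section 9.5.2.3) gives one row to "T4, TSH, AM Serum Cortisol, Testosterone, estradiol", at 6 mL per collection. Its time points are "Screening: 1 Visits 8, 11 (EOT), or ED", counted as three draws, or 18 mL of a 135 mL study total.

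Table 2 (Section 9.5.2.1) has separate lines for these analytes. The line "Testosterone, Estradiol" is marked at Screening, Visit 8 (Week 28) and Visit 11 (Week 52), and its ED cell is empty. The line "AM serum cortisol" is marked at Visit 2 (Day 1), Visit 11 and ED. The T4 and TSH line is marked at Screening, Visit 8, Visit 11 and ED.

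The text gives Table 2 authority over timing. Section 9.5.1.5.3 says that it "shows the visits and time points at which blood for clinical laboratory tests and urine for urinalysis will be collected", and Section 9.5.5 requires subjects who discontinue the study to complete the "early discontinuation procedures indicated in the Schedule of Procedures/Assessments". Footnote a to Table 2 adds: "Baseline measurements will be collected on Day 1, before drug administration unless specified otherwise".

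**The concern.** Section 8.2 names sex hormones and adrenal function among the safety objectives. The Synopsis evaluates sexual maturation by sex hormones together with Tanner Staging. Section 9.7.1.8.3 summarises every quantitative laboratory parameter as change from baseline to each later visit and to the last on-treatment value.

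A site that follows Table 2 exactly will examine Tanner stage and draw T4/TSH at the ED visit but will not measure testosterone or estradiol. Early leavers then contribute nothing to the hormone summaries after their last scheduled draw, and nothing post-baseline at all if they leave before Week 28. Table 3 meanwhile budgets for a hormone draw that is not scheduled and leaves out a cortisol draw that is.

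**Working it through.** **1. Table 3's own arithmetic.** 5×8 + 6×3 + 8×3 + 5×5 + 4×7 = 40 + 18 + 24 + 25 + 28 = 135 mL. The stated total is correct for the visits Table 3 lists.

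**2. The two tables side by side (v7.0).**

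| Analyte | Table 2 | Table 3 | Difference |
|---|---|---|---|
| T4, TSH | Screening, V8, V11, ED | Screening, V8, V11 or ED | none |
| Testosterone, estradiol | Screening, V8, V11 | Screening, V8, V11 or ED | ED in Table 3 only |
| AM cortisol | V2, V11, ED | Screening, V8, V11 or ED | V2 in Table 2 only; Screening and V8 in Table 3 only |

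The other Table 3 rows (routine laboratory tests, bone markers with lipids, prolactin with glucose, insulin and HbA1c, and PK) match Table 2 on scheduled visits and ED.

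**3. Is the blank cell a reading fault?** No. The neighbouring T4/TSH line keeps its ED mark, and Table 2 in v6.0 and v5.0 has the same blank.

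**4. Subjects affected by the blank ED cell.** Inputs from Section 9.7.2 are 260 randomised and 40% dropout, so 0.40 × 260 = 104. This is an upper bound, for three reasons:
- Subjects who only stop treatment are followed to study completion (Sections 9.1 and 9.5.5) and keep their remaining scheduled draws.
- Those who leave the study after Week 28 still have the Week 28 value.
- Those lost to follow-up or withdrawing consent may never attend an ED visit.

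**5. Blood volume.** Every draw counted in the 18 mL row does take place under Table 2, because T4/TSH need it. What is missing is the Visit 2 cortisol. As a full extra 6 mL draw, the row becomes 6×4 = 24 mL and the total 135 − 18 + 24 = 141 mL, or 6/135 = 4.4% more. No cortisol-only volume is given, and Table 3 already has 5 + 8 + 5 = 18 mL drawn at Visit 2, so the true addition may be smaller.

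**The case against.** The best defence is that there is a hierarchy. Table 2 is the schedule and Table 3 a volume summary that groups analytes by tube, so a site has one instruction to follow. This stands for cortisol. A reader might infer that the Day 1 cortisol baseline is lost, but that happens only if sites or laboratory kits work from Table 3. Even then a pre-dose Screening value would exist, and footnote a allows for exceptions to Day 1. The defence does not help for sex hormones: if Table 2 governs, the blank ED cell is what sites will follow.

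A reader might also take 104 as the expected loss, or assume uniform dropout over 52 weeks and report 104 × 28/52 = 56 subjects with no post-baseline value. The protocol states no dropout pattern, does not split treatment stoppers from study leavers, and gives no ED attendance rate. Neither figure can be read as an estimate. Nor does the document show that early leavers' hormone values differ from those of other subjects.

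It is also tempting to say that the 135 mL total rests on visits Table 2 does not use. It does not; the total only omits the Visit 2 cortisol.

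Two further points have some weight. Amendment 01 added cortisol and a pregnancy test at ED but not sex hormones, so the omission could be deliberate, though no reason is recorded. And the file shown is part 2 of 3, so a later version that corrects this cannot be excluded. Against the view that Table 3 is loose shorthand, the revision history shows the sponsor amending both tables together, for hormone timing in v5.0 and for ED cortisol in v6.0.

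**Conclusion.** The two tables contradict each other on testosterone/estradiol and on AM cortisol, and T4/TSH are unaffected. The practical consequence, taking Table 2 as controlling, is that subjects attending an ED visit give no closing sex-hormone value, and those leaving before Week 28 have no post-baseline one. The bound is 104 of 260 at the planned dropout, and the document supports nothing tighter. The blood total is understated by at most 6 mL, on the assumption that the Visit 2 cortisol needs its own full-size tube.

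This is an internal inconsistency that bears on descriptive safety summaries and sample logistics. No hypothesis test is planned for safety (Section 9.7.1.8), and the primary analysis is untouched. It is still worth correcting, because sex hormones are a named safety objective in adolescents and the correction is small.

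**What to change.** Reconcile the tables so that each analyte has a single visit list.

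- **Testosterone/estradiol:** either carry the ED draw that Table 3 already counts into the ED column of Table 2, or remove it from Table 3 and document why it is omitted. The first option adds no blood beyond the Table 3 budget, since EOT or ED is already one 6 mL draw and T4/TSH are taken at that visit.
- **AM cortisol:** give it its own entry in Table 3 at the Table 2 visits, state its tube volume, and restate the total (above 135 mL if the sample needs added volume, and up to 141 mL).
- **Kits:** check that the laboratory kits for Visit 2 and ED match the reconciled list.

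The cost is two table edits and a kit check, plus one added hormone assay per subject attending an ED visit if the first option is chosen.
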